5.3.2 Discontinuation of Study Drug

A patient must permanently discontinue treatment with study drug for any of the following reasons:

- The patient is withdrawn from the study ([Section 5.3.1](#)).

- The patient experiences a serious or intolerable AE (as defined in [Section 9](#)) that, in the Investigator's opinion, requires treatment discontinuation.
- A change in the patient's medical condition not consistent with the protocol requirements or that justifies withdrawal from the study or study drug
- Pregnancy (refer to [Section 10](#))
- Patients with renal, hepatic, platelets, clotting time, and inflammatory laboratory values that are severe (i.e., CTCAE Grade 3) or higher and/or considered clinically significant, in the opinion of the Investigator, will temporarily discontinue treatment and be retested every 2 weeks until resolution of laboratory abnormalities. Patients with renal or hepatic laboratory values that are serious (i.e., CTCAE Grade 4) will be permanently discontinued from treatment and will be retested every 2 weeks until resolution.

If a patient discontinues treatment, they will be encouraged to remain in the study to be monitored and to complete all study-related procedures, unless consent is withdrawn. Patients who discontinue treatment due to an AE ([Section 9](#)) or pregnancy ([Section 10](#)) may require longer follow-up.

The reason for discontinuation of treatment with study drug must be recorded in the eCRF and source documentation.

5.3.3 *Lost to Follow-up*

Patients who fail to return for final assessments will be contacted by the site in an attempt to have them comply with the protocol. A minimum of 3 documented contact efforts should be made on different days over the course of 2 weeks. If the patient is unreachable by telephone, a registered letter will be sent to the patient requesting him or her to contact the study center. If contact with the patient is not established after all above attempts, this patient will be considered as lost to follow-up.

5.3.4 *Replacements*

Patients will be replaced in accordance with the requirements for dose escalation.

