
The patient will be followed up for safety per protocol. Per the Investigator's judgement, the patient may be allowed to resume participation in the study if or when the event has resolved. Dosing may be resumed for individual patients upon recovery from the severe event and if supported by the Investigator, based on their assessment of the benefit/risk balance for the patient.
			

Adverse event terms related to lumbar puncture and administration (e.g., procedural pain, traumatic lumbar puncture, or post-lumbar puncture syndrome) will be exempted from the assessment of Stopping Criteria. A full list of AE terms exempt from the Stopping Criteria is provided in Section 4.4.3.4.
			

Number of Patients (Planned): Approximately 54 patients
			

Study Population: Patients must satisfy all of the inclusion and none of the exclusion criteria to be eligible for the study. Patients will be required to be prescreened to determine heterozygosity at SNP3 with the A variant only on the same allele as the CAG triplet expansion.
			

Inclusion Criteria:
 
1. Documented ability to understand the written study ICF(s) and consent and has provided signed written informed consent prior to any study procedures2. Ambulatory male or female3. Age ≥ 25 to ≤ 60 years old4. Body mass index (BMI) ≤ 32 kg/m²5. Documented CAG triplet repeats ≥ 36 in the HTT gene			

Sponsor: Wave Life Sciences Ltd.	Investigational Product: WVE-003	Developmental Phase:	EudraCT Number:

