4.4.3.3 Individual Stopping Criteria

Dosing will be stopped for an individual patient at any time in the study if:

- A patient experiences a serious or intolerable adverse event (AE) that, in the Investigator's opinion, requires study drug discontinuation.
- A patient experiences a TEAE that is severe in intensity and related to administration of WVE-003 (except TEAEs associated with lumbar puncture).

The patient will be followed up for safety per protocol. Per the Investigator's judgement, the patient may be allowed to resume participation in the study if or when the event has resolved]. Dosing may be resumed for individual patients upon recovery from the severe event and if supported by the Investigator, based on their assessment of the benefit/risk balance for the patient.

4.4.3.4 *Adverse Events That are Exempt from Stopping Criteria*

Intrathecal administration of drugs is known to result in untoward effects such as post-lumbar puncture headache, pain, etc.^{33,34} Given the common occurrence of such side effects following lumbar puncture, it is anticipated that patients may experience AEs temporal to the IT administration procedure that are not attributable to study drug^{33,34}. Therefore, the AE terms listed in [Table 5](#) will be exempted from the assessment of Stopping Criteria:

Table 5 Adverse Event Preferred Terms Exempted From Stopping Criteria

Preferred Terms Exempt From Stopping Criteria	
Administration site bruise	Instillation site bruise
Catheter site bruise	Post-lumbar puncture syndrome
Infusion site bruising	Post-procedural discomfort
Infusion site discomfort	Post-procedural contusion
Infusion site pain	Procedural headache
Injection site bruising	Procedural pain
Injection site discomfort	Traumatic lumbar puncture
Injection site pain	

Abbreviations: AE = adverse event; MedDRA = Medical Dictionary for Regulatory Activities; PT = Preferred Term.

Note: AEs exempted from the Stopping Criteria include the MedDRA PTs listed above and their associated verbatim terms.

While these procedural events are exempt from Stopping Criteria review, they will be recorded as AEs as described in [Section 9](#). In addition, as part of their ongoing review of unblinded safety data, the SMC will carefully review the above-referenced exempted AE terms to ensure there are no meaningful imbalances between treatment groups.

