8.2 Safety Assessments

The safety assessments will include the following:

- Adverse events ([Section 9](#))
- Medical history and demographics
- Prior and concomitant medications
- Physical examination (including neurological and psychiatric)
- Height and weight
- Vital signs
- 12-lead ECG
- Clinical laboratory evaluations (including clinical chemistry, hematology, and urinalysis)
- Cerebrospinal fluid safety laboratory evaluation
- Suicidality assessment
- Pregnancy testing (if applicable)
- Drug screening

Any abnormal laboratory test results (hematology, clinical chemistry, or urine) or other safety assessments (e.g., vital sign measurements) that are clinically significant in the medical and scientific judgment of the Investigator are to be recorded as AEs or SAEs.

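### Section 4.4.3.3 and the synopsis permit re-dosing after a severe related event without excepting the Grade 4 renal or hepatic values that Section 5.3.2 makes a permanent stop

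*Combined protocol and SAP*

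**What the plan says.** Section 4.4.3.3 (Individual Stopping Criteria) stops an individual's dosing on either of two triggers. The first is a serious or intolerable AE that the Investigator thinks requires discontinuation. The second is: "A patient experiences a TEAE that is severe in intensity and related to administration of WVE-003". The only exception to the second trigger is for events associated with lumbar puncture. The section then says: "Dosing may be resumed for individual patients upon recovery from the severe event and if supported by the Investigator", on the Investigator's view of benefit and risk. The synopsis has the same triggers and the same permission.

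Section 5.3.2 (Discontinuation of Study Drug) opens its list with "A patient must permanently discontinue treatment with study drug for any of the following reasons". Its last bullet holds two laboratory rules:

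- Patients whose renal, hepatic, platelet, clotting-time or inflammatory values are Grade 3 or higher, and/or clinically significant in the Investigator's opinion, "will temporarily discontinue treatment and be retested every 2 weeks until resolution of laboratory abnormalities".
- For two of these five categories, a stricter rule applies one grade up: "Patients with renal or hepatic laboratory values that are serious (i.e., CTCAE Grade 4) will be permanently discontinued from treatment". The Investigator's opinion plays no part in this second rule.

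Section 8.2 links laboratory values to adverse events: abnormal results that are "clinically significant in the medical and scientific judgment of the Investigator are to be recorded as AEs or SAEs".

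**The concern.** An individual stopping rule should give one answer for one patient. Here one section makes an event a permanent stop, and another allows dosing to restart after recovery on the Investigator's support alone, without excepting that event. A site working from the synopsis or Section 4.4.3.3 could give an intrathecal dose that Section 5.3.2 forbids, in what Section 1.4 calls the first clinical study of WVE-003.

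Two other controls may not catch a first case. Safety laboratory tests are done up to a week before each Period 2 dose (Table 4 footnote), but a value that has recovered would not reveal the earlier Grade 4 result. The Period 2 cohort halt in Section 4.4.3.2 needs two patients, so the individual rule decides whether a single affected patient is dosed again.

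**Working it through.** The plan states no figure to reproduce. The check compares the two rules and then counts doses.

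**1. Side by side**

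| | Section 4.4.3.3 and synopsis | Section 5.3.2, Grade 4 sentence |
|---|---|---|
| Trigger | Severe TEAE related to WVE-003 | Grade 4 renal or hepatic value |
| Exceptions | Lumbar-puncture events only | None |
| After recovery | Dosing may restart | Permanent stop |
| Who decides | Investigator | Nobody; the rule is fixed |
| Cites the other | No | No |

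**2. Can one event meet both triggers?** Yes, if three conditions hold.

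- The value is recorded as an AE. Section 8.2 requires this when the Investigator finds it clinically significant.
- The AE is rated severe. Table 7 has three levels and Severe is the highest. The rating is not automatic: Section 9.2.1 grades effect on daily activities rather than CTCAE level, and Table 7 places asymptomatic findings and purely diagnostic observations under Mild.
- The AE is judged related to WVE-003.

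**3. Outcome when both triggers are met.** After recovery, Section 4.4.3.3 permits another dose and Section 5.3.2 forbids it. Withholding drug for good complies with both; re-dosing breaches Section 5.3.2. No section states which rule prevails.

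**4. Doses at stake in P2C1.** Section 4.1.4.3 places doses at Weeks 0, 8 and 16, so there are 3. Doses remaining after dose k = 3 − k:

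- event after dose 1: 3 − 1 = 2
- event after dose 2: 3 − 2 = 1
- event after dose 3: 3 − 3 = 0

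**5. The laboratory bullet.** It names 5 categories. Two (renal, hepatic) have an explicit permanent rule at Grade 4. The other 5 − 2 = 3 (platelets, clotting time, inflammatory) have only the temporary instruction, although it sits under a lead-in that requires permanent discontinuation.

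**The case against.** The strongest reply is that these are not two incompatible orders. Section 4.4.3.3 grants a discretion, while Section 5.3.2 gives a specific, mandatory rule. Section 5.3 adds that patients who discontinue treatment receive no more study drug, and Section 13.4 binds the Investigator to the whole protocol. Read together, the compliant course is not to re-dose. This largely stands and keeps the severity low. It does not remove the defect, because the reader must infer a precedence that the protocol never states.

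Second, several judgements must line up: the value is recorded as an AE, rated severe, judged related and resolved, and an Investigator who has overlooked Section 5.3.2 then supports re-dosing. That also stands, which is why the point is limited to such cases.

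Third, other safeguards exist. SAEs reach the Sponsor within 24 hours (Section 9.3.4.1), the SMC reviews unblinded safety data (Section 4.4.2), the Sponsor may withdraw any patient (Section 5.3.1), and in Period 1 a single related SAE suspends the cohort (Section 4.4.3.1). These reduce the risk, but none settles which individual rule governs.

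A reader might infer four stronger points that the documents do not support:

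- *The two-weekly retests show that patients could be cleared in time for the next dose.* For Grade 4 renal or hepatic values, the sentence that orders the retests also orders the permanent stop, so a site following it has the prohibition in view. The documents give no recovery time.
- *Every serious or intolerable AE is in conflict.* The Section 5.3.2 bullet applies only where the event, in the Investigator's "opinion, requires treatment discontinuation". A conflict over dosing needs an event that is also severe and related, and an Investigator who reverses that judgement. This is a narrow case.
- *The temporary hold under a permanent lead-in is a second safety conflict.* The bullet itself says which values are temporary and which permanent. Its own words are the natural reading, so it is a misplaced rule.
- *Up to three Period 2 doses are exposed for a patient affected in Period 1.* Rollover requires the separate eligibility check in Section 4.1.4.1, made by the Investigator in consultation with the Sponsor, so those doses are not counted here.

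**Conclusion.** Wrong as written: conflicting patient-safety rules, of low severity. The permission to restart dosing in Section 4.4.3.3 and the synopsis has no exception for events that Section 5.3.2 makes permanent, in particular Grade 4 renal or hepatic values.

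The size is bounded by dose count only: at most 2 further doses per affected P2C1 patient after dose 1, and 1 after dose 2. No rate can be given. The conclusion assumes that the Grade 4 value has been recorded as an AE, rated severe and judged related; without all three, the severe-TEAE trigger is not met and this conflict does not arise. No sample size, endpoint or analysis is affected.

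**What to change.** In Section 4.4.3.3 and the synopsis, add to the sentence on restarting dosing: *except where Section 5.3.2 requires permanent discontinuation (including Grade 4 renal or hepatic laboratory values)*. Cross-reference Sections 4.4.3.3 and 5.3.2 to each other.

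As a secondary editorial change, move the temporary laboratory hold to its own heading for temporary interruption, and leave the Grade 4 renal or hepatic rule in the permanent list.

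The cost is one clause in two places, the cross-references, one new heading and a note to sites. No procedures, data collection or patients are added. If the change is regarded as more than a minor clarification, Section 15.3.1 also requires IRB/EC and regulatory submission; it could then be made with the next amendment, with sites told of the intended reading beforehand.

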6 INVESTIGATIONAL DRUG AND PLACEBO

6.1 Method of Assigning Patients to Investigational Drug or Placebo

Patients who qualify according to all of the inclusion and exclusion criteria will be randomized into the study. Treatment will be assigned through randomization performed using a centralized, interactive voice/web response system.

6.2 Dose and Investigational Drug/Placebo Administration

6.2.1 Identity of Investigational Drug

6.2.1.1 WVE-003

WVE-003 will be provided as lyophilized powder for reconstitution and dilution for IT injection. WVE-003 for injection will be prepared by reconstituting and diluting the lyophilized powder with aCSF supplied by the Sponsor. Directions on reconstitution and dilution are provided in the Pharmacy Manual.

Laboratory Code: WVE-003

Chemistry: WVE-003 can be described chemically as the fully neutralized sodium salt of a 3'→5' linked mixed 2'-O-(2-methoxyethyl)-2'-deoxy-/ 2'-O-methyl ribonucleic acid oligonucleotide 20 mer, containing a prescribed combination of stereodefined Sp and Rp phosphorothioate diester, stereodefined Rp N-(1,3-dimethylimidazolidin-2-ylidenyl) phosphoramidate diester, and phosphodiester internucleotide linkages.

International Nonproprietary Name: Not yet assigned

6.2.1.2 Placebo

Placebo will be aCSF provided by the Sponsor. It will be a sterile, preservative-free solution. Placebo will be visually identical in appearance to the WVE-003 injection solution and administered intrathecally in order to maintain the blind. Placebo will be administered in a volume of 20 mL.

6.2.2 Administration of Investigational Drug

Study drug (WVE-003 or placebo) will be administered by IT injection by direct lumbar puncture using an atraumatic needle, and the total volume of the injection will be 20 mL. WVE-003 will be diluted with aCSF provided by the Sponsor and administered in a volume of 20 mL, as described in the Pharmacy Manual. The lumbar puncture will be performed by a physician who is experienced in lumbar puncture procedure and drug administration and appropriately trained for the study. Within 1 week prior to the lumbar puncture, a blood sample will be tested locally for platelet count and prothrombin time to confirm that it is safe to proceed with the lumbar puncture ([Section 8.2.8](#)). Patients should not be sedated during administration of study drug. Imaging is allowed to guide lumbar puncture if needed. Detailed instructions on the procedure to be used for lumbar puncture are provided in the Study Operations Manual.

Within approximately 15 minutes prior to administration of study drug, CSF samples will be collected for safety assessments ([Section 8.2.8](#)), concentration of WVE-003 ([Section 8.3](#)), and PD ([Section 8.4](#)), per the Schedule of Assessments. Additional CSF collected will be stored and used for research purposes. Approximately 20 mL of CSF total should be collected.

Immediately after each administration of study drug, all patients should be ambulatory and active for approximately 30 minutes postdose. The Investigator should note any weakness or fatigue during this period. In addition, formal physical examinations targeting the neurological system will be performed at the time points noted in the Schedule of Assessments. Any postdose SAEs will be monitored until resolution.

6.3 Treatment Compliance

Provided that a patient attends the clinic visits, treatment noncompliance is not expected to be an issue. Thus, every attempt will be made to ensure regular visits by the patient to the clinic per the study schedule. Investigative staff will make every effort to contact patients who miss visits in order to obtain as much follow-up information as possible.

6.4 Management of Clinical Supplies

6.4.1 Investigational Drug Packaging and Storage

WVE-003 will be supplied by the Sponsor as a lyophilized powder in clear glass vials. Artificial CSF (placebo and diluent for WVE-003) will be supplied in single-use vials provided by the Sponsor for investigational use only.

All study drugs will be transported, received, stored, and handled in accordance with the container or product label, the instructions supplied to the pharmacy, relevant institution's Standard Operating Procedures (SOPs), and applicable regulations. Appropriate storage and transportation conditions will be maintained for the study drug from the point of manufacture up to delivery of the study drug.

Study drugs will be stored at 2°C to 8°C in a locked area accessible only to the pharmacy personnel until reconstitution. Both the WVE-003 for injection and aCSF placebo contain no preservatives and should be administered without delay or within 4 hours of reconstitution/preparation.

Partially used, unused, or damaged vials should be disposed according to Sponsor instructions.

Details on reconstitution and administration are provided in the Pharmacy Manual.

6.4.2 Study Drug Accountability

The Investigator will maintain accurate records of receipt of drug supplies, including dates of receipt. In addition, accurate records will be kept regarding when each treatment is administered, which patients received treatment, and the name of the personnel administering the treatment. Reasons for departure from the expected treatment regimen must also be recorded. Only trained site staff are permitted to treat study patients. A study monitor will review the accountability records.

6.4.3 Other Supplies

The study sites will be provided with the IB, Study Operations Manual, Pharmacy Manual, Imaging Manual, Laboratory Manual, laboratory kits, and other materials, as appropriate.

7 BLINDING AND RANDOMIZATION

7.1 Blinding

In order to maintain the blinding of the study drug (placebo or investigational product), all study personnel will be blinded to patient treatment assignment. Physicians, nurses, patients, and any study personnel performing patient assessments must NOT be informed of the patient's treatment assignment except in the event of a medical emergency or as required by regulatory authorities ([Section 7.2](#)).

The Sponsor and CRO staff directly responsible for the conduct of the study, the Investigator, and site staff will be blinded to treatment for the duration of the study until database lock.

The pharmacy personnel will be unblinded to prepare doses of investigational product or placebo to ensure that the patient and the clinical site staff responsible for administering study drug and conducting assessments per the protocol remain blinded to study treatment. In addition, a clinical research associate will be unblinded to perform drug accountability.

7.2 Breaking the Blind

7.2.1 Unblinding for Medical Emergency

A patient's treatment assignment should remain blinded until the end of the study. However, in the event of a medical emergency when the medical treatment of the patient depends on knowing the study treatment the patient received, the treatment blind may be broken through the IRT system. The Investigator must document the reasons for unblinding in the patient's source documents. *The Investigator is strongly advised not to divulge the patient's treatment assignment to any individual not directly involved in managing the medical emergency nor to personnel involved with the analysis and conduct of the study.*

7.2.2 Recording the Unblinding

If an unblinding occurs, the date on which the code was broken, together with the identity of the person responsible for breaking the blind, must be documented in the patient's source documents. The unblinded treatment information will not be disclosed to the Sponsor. In consultation with the Medical Monitor and the Sponsor, the patient may be withdrawn from the study, if the blind is broken.

The documentation should include, but is not limited to, the following information:

- Patient information

- Reason for unblinding
- Date and time of unblinding
- Name of the person requesting/responsible for unblinding

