3 STUDY OBJECTIVES

Primary Objective:

- To evaluate the safety and tolerability of WVE-003 in patients with HD

Secondary Objectives:

- To characterize the PK of WVE-003 in plasma
- To characterize the concentration of WVE-003 in CSF

Exploratory Objectives:

- To evaluate the PD effect of WVE-003 on the levels of mHTT protein in CSF
- To evaluate the effect of WVE-003 on clinical measures of disease including the Unified Huntington's Disease Rating Scale (UHDRS) and Short Problem Behaviors Assessment (PBA-s)
- To evaluate the PD effects of WVE-003 on relevant biomarkers in CSF, plasma, and peripheral blood mononuclear cells (PBMCs) (e.g., levels of wtHTT protein, total huntingtin [tHTT] protein in CSF, and neurofilament light [NfL] in CSF and plasma)
- To evaluate changes from baseline in magnetic resonance imaging (MRI) of the brain

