11.3.4 Analysis of Safety Data

The summary of safety results will be presented by dose group. All safety analyses will be performed on the safety population using the following common rules:

- The baseline value is defined generally as the last available value before randomization.
- Adverse event observation periods are defined as follows:
 - Pretreatment AEs are AEs that developed or worsened prior to the first dose of study drug.

- On-treatment adverse events are AEs that developed or worsened from the first dose of study drug to study completion/discontinuation. Summaries of TEAEs will include all on-treatment AEs.
- For quantitative safety parameters based on central laboratory/reading measurement, descriptive statistics will be used to summarize results and change from baseline values by visit and treatment group.

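### Section 7.2.2 lets a broken blind end a patient's study participation, so safety follow-up can be cut short for a reason linked to safety events

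*Combined protocol and SAP*

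**What the plan says.** The primary objective (Section 3) is "To evaluate the safety and tolerability of WVE-003 in patients with HD".

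**Breaking the blind.** Section 7.1 bars disclosure of the assignment "except in the event of a medical emergency or as required by regulatory authorities". Section 7.2.1 then sets out a single procedure: the site may break the blind through the IRT "in the event of a medical emergency when the medical treatment of the patient depends on knowing the study treatment the patient received". Section 7.2.2 adds: "In consultation with the Medical Monitor and the Sponsor, the patient may be withdrawn from the study, if the blind is broken". It gives no criterion for when withdrawal should follow. The same paragraph keeps the assignment from the Sponsor.

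**Leaving the study or stopping drug.** The list of mandatory withdrawal reasons in Section 5.3.1 does not include unblinding, but the section also gives the Sponsor open discretion to withdraw any patient. Section 5.3.2, on stopping study drug, says: "If a patient discontinues treatment, they will be encouraged to remain in the study to be monitored and to complete all study-related procedures".

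**Safety window.** Section 11.3.4 states: "On-treatment adverse events are AEs that developed or worsened from the first dose of study drug to study completion/discontinuation". Summaries of TEAEs are built from that window.

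**The concern.** The documented route to a broken blind is an emergency, and in many cases that emergency will itself be a safety event. If the broken blind is then a ground for leaving the study, observation for the primary objective can stop early in a patient because something serious happened to that patient. Follow-up time would then no longer be independent of the safety experience it is meant to measure.

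Unblinding gives little scientific reason for that exit. Knowing the assignment does not spoil a laboratory value, a CSF cell count or a centrally read MRI. It can colour judgements such as rating scales and causality, but those can be identified and examined separately.

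At stake are later events in a few patients of particular safety interest, in a first-in-human study with small cohorts. The AE tables in Section 11.3.4.1 give numbers and percentages of patients, with no adjustment for shortened follow-up.

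**Working it through.** The plan has no figure to reproduce. Section 11.1 bases the sample size on no hypothesis test, and no expected number of unblindings is given. The check is a comparison of sections, followed by arithmetic for scale.

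**1. What ends and what continues after withdrawal from the study**

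| Item | After withdrawal | Source |
|---|---|---|
| SAE already under way | Followed to resolution, whatever its relationship to drug | 9.3.1, 9.3.3 |
| Events already recorded | Stay in the safety population's data and can count toward stopping criteria | 11.2.1, 4.4.2, 4.4.3 |
| Final assessment | One early termination visit expected; its lumbar puncture is optional | 4.1.5, Tables 2 and 4 |
| Later scheduled examinations, laboratory tests, CSF safety samples, C-SSRS, MRI | Stop | 4.1.5, 4.2 |
| Ongoing non-serious AEs | Required follow-up ends at ET or EOS | 9 |
| TEAE window | Closes | 11.3.4 |
| New SAE judged related | Reported to the Sponsor, not entered in the eCRF | 9.3.4.1 |
| New SAE judged unrelated | Need not be reported after the final follow-up visit | 9.3.1 |

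The triggering event is therefore covered. What is lost is scheduled surveillance for later events, and their entry into the tables.

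**2. Comparison with the rest of the protocol**

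Section 5.3.2 separates stopping drug from leaving the study and favours staying. Section 10 does the same for pregnancy: drug stops, but the patient may still be followed. Section 7.2.2 goes the other way, without a stated reason.

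**3. Scale, for illustration**

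Inputs: planned Period 1 sizes and the 2:1 ratio (Section 2.3); the 12-week minimum Period 1 follow-up (Section 4.1.3.2); P2C1 of about 24 patients (Section 4.1.4.2); Period 2 visits to Week 28 (Table 3).

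- P1C3 active patients: 12 × 2/3 = 8. One patient is 1/8 = 12.5%.
- P1C1 and P1C2 active patients: 18 × 2/3 = 12 each. One patient is 1/12 = 8.3%.
- Chosen scenario, exit at Week 2 with all others completing 12 weeks: the patient loses (12 − 2)/12 = 83% of minimum follow-up. As a share of the active group's patient-time, this is 0.833/8 = 10.4% in P1C3 and 0.833/12 = 6.9% in a group of 12.
- P2C1, both arms together: 1/24 = 4.2%. No Period 2 randomization ratio is stated, so an active-arm share cannot be derived.
- Period 2 visits lost: up to 28 − 0 = 28 weeks if exit is just after the first dose, or up to 28 − 16 = 12 weeks if just after the Week 16 dose.

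**4. Is the lost time relevant to drug effects?**

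Section 5.2.1.2 equates 5 months with 5 elimination half-lives, so one half-life is about 1 month. Assuming simple first-order decline, 2^(−0.5) = 0.71, so about 70% of drug would remain half a month after a dose. The section does not say which compartment the half-life describes, so this is only indicative. It suggests that a patient leaving at Week 2 may still be materially exposed.

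**The case against.** The strongest case against is that this is a permissive clause with safeguards around it. Withdrawal is optional and follows consultation, and the Sponsor does not know the assignment, which limits selective withdrawal by arm on its side. The event that led to unblinding is recorded, followed and open to SMC review. Late related SAEs still reach the Sponsor. No unblinding rate is given, so the expected loss may be nil. All of this stands and limits the size of the point.

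Several stronger readings are tempting but not supported:

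- *The blind can be broken only in an emergency.* Section 7.1 also allows disclosure required by regulatory authorities. The emergency is the only procedure that Section 7.2 describes.
- *The patients with the gravest events lose their safety follow-up.* Many SAEs would not need unblinding, some emergencies will be unrelated to drug, and the event itself is followed to resolution. Only later surveillance is at risk.
- *The primary data become missing not at random.* That would need withdrawals that may never occur. The MMRM in Sections 11.3.2 and 11.3.3 serves exploratory endpoints, not the primary safety objective.
- *Section 7.2.2 contradicts Section 5.3.2.* Section 5.3.2 encourages patients who stop drug to remain; it does not forbid study withdrawal. The two pull in different directions without conflicting outright.
- *Deleting the sentence is enough.* Section 5.3.1 would still let the Sponsor withdraw a patient for any reason.

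The objection does not supply a reason why unblinding should end safety follow-up. Discretion limits how often it happens but sets no criterion that protects the data.

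**Conclusion.** The point holds in limited form. As written, Section 7.2.2 makes a broken blind a ground for leaving the study. Because the described route to unblinding is an emergency, follow-up for the primary objective can be shortened for a reason linked to safety events. The loss is of scheduled visits after exit, of new events outside the TEAE window, and of eCRF entry for related SAEs that start later.

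The size is illustrative. One patient is 12.5% of planned active patients in P1C3 and about 4% of P2C1. The patient-time figure of about 10% rests on a chosen early exit in the smallest planned cohort and is not an expected loss. Any imbalance between arms would depend on the drug causing such emergencies, or on site staff who know the assignment influencing withdrawal; the documents show neither. The change is worth making in the next amendment because it protects primary safety data at little cost.

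**What to change.** - **Section 7.2.2:** replace the withdrawal sentence with a statement that unblinding alone is not a reason for withdrawal from the study, and that the patient stays in scheduled safety follow-up, subject to consent and the existing medical-reason provision in Section 5.3.1. Whether study drug continues stays with the existing provisions.
- **Sections 5.3.1, 5.3.2 and 7.2.2:** reconcile them, including the Sponsor's discretion to withdraw for any reason, so that the new statement is not overridden elsewhere.
- **eCRF and analysis plan:** flag judgement-based data collected after unblinding (UHDRS, PBA-s, C-SSRS and Investigator causality ratings), with a sensitivity analysis that leaves out the flagged rating-scale scores.

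The cost is a short wording change in the next amendment and one eCRF flag. The downside is a few assessments and causality ratings made with knowledge of treatment. Causality ratings feed the stopping criteria, so this matters; the flag identifies such data but does not remove the possible bias.
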